16. DATA HANDLING AND RECORD KEEPING

All raw data generated in connection with this study (and site files), together with the original copy of the final report, will be retained in the archives of until at least five years after the last approval of a marketing application in an ICH region and until there are no pending or contemplated marketing applications in an ICH region or at least five years have elapsed since the formal discontinuation of clinical development of BoNT/A-DP. These documents will be retained for a longer period if required by the applicable regulatory requirements, or by an agreement with the Sponsor. The trial master file (TMF) will be archived by the Sponsor.

The study site should maintain a study file, which should contain, at minimum, the IB, the protocol and any amendments, drug accountability records, correspondence with the Independent Ethics Committee (IEC)/Institutional Review Board (IRB) and the Sponsor (or designee), and other study-related documents.

The investigator agrees to keep records and those documents that include (but are not limited to) the identification of all participating subjects, medical records, study-specific source documents, source worksheets, all original signed and dated ICFs, copies of all CRFs, query responses, and detailed records of drug disposition to enable evaluations or audits from regulatory authorities.

The investigator should retain records required to be maintained for a period of five years following the date a marketing application in an ICH region is approved for the drug for the indication for which it is being investigated or, if no application is to be filed or if the application is not approved for such indication, until at least five years after the investigation is discontinued. However, these documents should be retained for a longer period if required by the applicable regulatory requirement(s) or if needed by the Sponsor. In addition, the investigator must make provision for the subjects' medical records to be kept for the same period of time.

No data should be destroyed without the agreement of Croma-Pharma GmbH. Should the investigator wish to assign the study records to another party or move them to another location, Croma-Pharma GmbH must be notified in writing of the new responsible person and/or the new location.

Subjects' medical records and other original data will be archived in accordance with the archiving regulations or facilities of the investigational site.

16.1 Confidentiality Policy

The investigator and all personnel involved in the trial will maintain a policy of confidentiality.

16.2 Source Documentation and Case Report Forms

Data will be recorded at sites using CRFs and reviewed during monitoring visits. The recorded data in the EDC system will be verified with source documents. All corrections or changes made to any study data will be appropriately tracked in an audit trail in the EDC system. CRFs will be considered complete when all missing, incorrect, and/or inconsistent data has been accounted for. Data collected at screening will be reported in CRFs, regardless of screening outcome.

Source data (e.g. clinical laboratory reports, ECG printouts) should bear the study number, subject number, date of data generation, and, if reviewed, dated signature of the investigator or designee. Adverse events, concomitant medication data and clinical observations will be in the subjects' hospital notes, or recorded on source data forms, and will be transferred into the CRF after assessment by the investigator or designee.

Other data of medical measurement without print-outs (date and time of study activities, i.e. time of blood sampling, administration of study medication) performed during the study will be captured on the respective laboratory requisition forms or dispensing/administration log, which will serve as source documentation for the respective activities. Data produced by automatic devices with original print-outs (e.g. clinical laboratory test results, ECG traces, blood pressure measurements) will be included in the source documentation. Clinical laboratory parameters will be provided in laboratory print-outs which are to be reviewed, signed and dated by the investigator or designee. Any results outside the normal range should be assessed for clinical significance. The investigator will maintain complete and accurate study documentation in the Investigator Site File.

The investigator will comply with the procedures for data recording and reporting. Any corrections to source documentation must be performed as follows: 1) the first entry will be crossed out entirely, remaining legible; 2) if not self-evident a reason for the change must be given; and 3) each correction must be dated and initialed by the person correcting the entry; the use of correction fluid and erasing are prohibited.

16.2.1 Case Report Forms

The investigator is responsible for the procurement and the quality of source data.

Authorized study site personnel will transcribe source data and source data changes to the CRF. All data should preferably be entered into the CRF on the day of the study visit, but no later than 2 working days thereafter. Changes to a CRF, if not self-evident, will require documentation of the reason for each change. After completion of the study, an electronic (or if necessary paper) version of the complete set of CRFs for each subject will remain in the investigator file at the study site in accordance with the data retention policy (see Section 16.3).

The handling of data by the Sponsor, including data quality assurance, will comply with regulatory guidelines (e.g.Code of Federal Regulation (Title 21, CFR Part 312)). All data management activities will be conducted by the Sponsor's representative who will follow their SOPs. Data management and control processes specific to the study will be described in the Data Management Plan.

Once all the Data Quality Control steps have been performed, the database will be locked and the records will be released for reporting and statistical analysis. Data will be transferred to the study sites via CDs and transferred to the study Sponsor via an external hard drive. The media will contain subject PDF files of the electronic CRFs.

16.2.2 Computer Systems

Data will be processed using a validated computer system conforming to regulatory requirements.

16.2.3 Data Entry

Data must be recorded using the EDC system. All study site personnel must log into the system using their secure user name and password in order to enter, review, or correct study data. These procedures must comply with the Title 21 Code of Federal Regulations (21 CFR Part 11). All passwords will be strictly confidential.

16.2.4 Medical Information Coding

For medical information, the following thesauri will be used:

- Latest version of MedDRA for medical history and AEs.
- WHO drug information for concomitant medications.

16.3 Document and Data Retention

The investigator will retain study documentation and data (paper and/or electronic forms) in accordance with applicable regulatory requirements and the data retention policy, as described in the Clinical Study Agreement.

The medical files of study subjects must be retained in accordance with local legislation and in accordance with the maximum period of time permitted by the hospital, institution or private practice.

16.3.1 Data Base Lock

Two data base locks will be performed, one after all subjects finalized the double blind phase (see section 12.5.2) and one after all data of the first treatment cycle and of the open label extension phase are entered into the CRF. In both cases the data base will be locked as soon as the respective data base is confirmed as 'clean'. Before the data base lock for the double blind phase, a data review meeting will take place. Further details will be described in the Data Management Plan.

17. FINANCING AND INSURANCE

The investigator will comply with investigator financing, investigator/Sponsor insurance, and subject compensation policies, if applicable, as described in the Clinical Study Agreement.

18. PUBLICATION POLICY

The investigator will comply with the publication policy as described in the Clinical Study Agreement.

19. REVISION HISTORY

Version	Date	Reason for Revision
Final	17.12.2018	N/A (original document)
Version		
Final	15.07.2019	- Reordering of secondary study objectives
Version	15.07.2019	- Reordering of secondary study objectives - Key secondary endpoints "percentage of responders at maximum frown at week 12 (after the first treatment)", "percentage of responders at week 16 (after the first treatment)", and "proportion of subjects with a ≥ 1 point reduction in FWS score at rest at week 4 in the first treatment cycle" are now set as additional secondary endpoints, but not as key secondary Clarification on Analysis sets: - The FAS will contain all randomized patients, no injection with study medication needed The MFAS includes all randomized subjects who received at least one injection with study medication who had a baseline visit 1 at day 0 and at least one post-dose in-clinic assessment with the FWS by either the investigator or the subject on visits at weeks 1, 2 or 4 The PP includes all randomized subjects who received at least one injection with study medication who had no significant protocol deviations and an inclinic assessment with the FWS by the investigator and the subject at baseline (day 0) and at the week 4 visit. For the PP, all subjects will be assigned to the randomized treatment actually receivedSubgroup analysis by site, country and geographic region (US versus EU) was added - Addition of Subgroup analysis for the primary efficacy endpoint - For secondary endpoint 4 all subgroup analyses as described for the primary endpoint will be conducted. For the proportion of subjects with ≥ 1 point reduction in FWS score during the first treatment cycle at week 12, 16 and 20 relative to baseline subgroup analyses by site, by country, by geographic region and by subjects with previous use of botulinum toxin versus naïve subjects will be conducted.
		- Physical examination assessment will also be done on each End of Cycle Visit
		- Addition of the following clarification regarding AESI questioning:
		30-minute post IMP administration, general, non-leading AE questioning as well as active AESI questioning must be performed
		- Clarification on subject Identification code:
		A SIC will automatically be assigned by the IWRS system at screening, which
		will comprise B3 (denoting the BLESS III study), followed by a single digit

Version	Date	Reason for Revision
		country identification, a two digit site identification and a three digit subject identification number -Update of emotional and Social functioning: Domain and overall scores will be calculated if at least two of three social and of at least two of four emotional domain items are present.

20. SUPPLEMENTS

[figure not shown]
20.1 Glabellar Line Scale - Subject (GLS-S)

- Glabellar lines, also known as frown lines, are the vertical wrinkles between your eyebrows that may appear worse when you frown.
- In this questionnaire you will be asked to rate the severity of your glabellar lines (how deep they are) when your face is relaxed (at rest) and then when you are frowning.
- Please use the accompanying drawings and the photo atlas to help you make your ratings.
- Not everyone's lines are the same on both sides of their face. Please use your most severe line to score the questionnaire.

1) Line severity at rest

- Please look directly in a mirror in a well-lit room with nothing obstructing your face (for example, tie back your hair or use a hairband, remove any make up and ensure your glasses do not obstruct the area between your eyebrows) and rate the lines between your eyebrows as they appear when your face is relaxed (at rest).
- Check the most appropriate scale score in the table below:

2) Line severity when frowning

- **Now please frown** (push your eyebrows together as far as they will go, as if you are feeling angry, using your facial muscles not your fingers) and look in the mirror. How would you rate the lines between your eyebrows now?
- Check the most appropriate scale score in the table below:

20.2 Glabellar Line Scale – Investigator (GLS-I)

- In this questionnaire you will be asked to rate the severity of the patient's glabellar lines when their face is at rest and when they are at maximum frown.
- Please use the accompanying drawings and the photo atlas to help you make your ratings.
- If the patient has any asymmetry in their glabellar lines, please use the most severe line to score the questionnaire.

1) Line severity at rest

Ask the patient to remove anything obstructing their forehead area (for example glasses and make-up, and tie back their hair or use a headband if necessary). In a well-lit room, and when the patient is looking directly at you, please rate the severity of the patient's glabellar lines at rest:

2) Line severity at maximum frown

Please now rate the severity of the patient's glabellar lines at maximum frown (asking the patient to push their eyebrows together as far as they will go):

20.3 GL-QoL (Modified Skindex-16)

During the past week how much have your glabellar lines bothered you? Glabellar lines are the vertical lines between your eyebrows that are more noticeable when you frown.

For each question please check the box from 0 (Never bothered) to 4 (Always bothered) that best represents how much the lines between your eyebrows have bothered you. If the question is not relevant to you, please check 'Never bothered'.

[figure not shown]

20.4 FACE-Q Appraisal of Lines Between Eyebrows Scale

FACE-Q APPRAISAL OF LINES-BETWEEN EYEBROWS

These questions ask about how you look right now. For each question, circle only one answer. With the area between your eyebrows in mind, in the past week, how much have you been bothered by:

FACE-Q © 2013. All Rights Reserved.

20.5 FACE-Q Age Appraisal VAS Scale⁴⁴

[figure not shown]
FACE-Q AGE APPRAISAL-VAS

We would like to know how old you think you look. How many years younger or older do you think you look compared with your actual age? Please circle one number below:

20.6 FACE-Q Satisfaction with Outcome Scale 45

FACE-Q © 2013. All Rights Reserved

20.7 Subject BMI Formula and Calculation

Table 20-1 BMI Formula and Calculation		
Measurement Units	BMI Formula and Calculation	
Kilograms and meters	Formula: weight (kg) / [height (m)] ² Calculate BMI by dividing weight in kilograms (kg) by height	
	in meters (m) squared	
Pounds and inches	Formula: weight (lb) / [height (in)] ² × 703 Calculate BMI by dividing weight in pounds (lb) by height in inches (in) squared and multiplying by a conversion factor of 703.	

BoNT/A-DP	CROMA-PHARMA GmbH's BoNT/A Drug Product registered in Korea under the name "Botulax"
CETS	Composite Endpoint Treatment Success
CFR	Code of Federal Regulations
CI	Confidence Interval
CMH	Cochran-Mantel-Haenszel
CRA	Clinical Research Associate
CRF	Case Report Form
CS	Clinically Significant
CSR	Clinical Study Report
DRM	Data Review Meeting
ECG	Electrocardiogram
eCRF	Electronic Case Report Form
EOS	End of Study
EU	European Union
FAS	Full Analysis Set
FDA	Food and Drug Administration
FWS	Facial Wrinkle Scale
GCP	Good Clinical Practice
GL-QoL	Glabellar Line Quality of Life Scale
GLS-I	Glabellar Line Scale for Investigators
GLS-S	Glabellar Line Scale for Subjects
IA	Interim Analysis
ICF	Informed Consent Form
ICH	International Council for Harmonization
IMP	Investigational Medicinal Product
ITT	Intent-to-treat

	Statistical Analysis Plan (SAP)	 <small>est. 1976</small>
--	--	---

IWRS	Interactive Web Response System
LOCF	Last Observation Carried Forward
MedDRA	Medical Dictionary for Regulatory Activities
MFAS	Modified Full Analysis Set
NCS	Not Clinically Significant
PRO	Patient Reported Outcome(s)
PP	Per-protocol Analysis Set
PT	Preferred Term
ROS	Review of Systems
SAE	Serious Adverse Event
SAF	Safety Analysis Set
SAP	Statistical Analysis Plan
SD	Standard Deviation
SDTM	Study Data Tabulation Model
SOC	System Organ Class
SOPs	Standard Operating Procedures
TC	Telephone Call
TEAE	Treatment Emergent Adverse Event
TFLs	Tables, Figures, and Listings
US	United States
VAS	Visual Analog Scale

	Statistical Analysis Plan (SAP)	CROMA est. 1976
---	--	---------------------------

1 INTRODUCTION

The purpose of this SAP is to provide detailed descriptions of the statistical methods, data derivations and data displays for study protocol CPH-303-201400 Version 2.0 “Randomized double blind Phase 3 study to assess the efficacy and safety of BoNT/A-DP in the treatment of glabellar lines in comparison with placebo followed by an open label extension study” dated 15 Jul 2019 for the planned interim and final analyses. The table of contents and templates for the tables, figures, and listings (TFLs) will be produced in a separate document.

Any deviations from this SAP will be described and justified in the Clinical Study Report (CSR).

The preparation of this SAP has been based on International Conference on Harmonization (ICH) E9 guideline and the Code of Federal Regulations (CFR) 21, part 11.

All data analyses and generation of TFLs will be performed using SAS 9.4® or higher.

	Statistical Analysis Plan (SAP)	 <small>est. 1976</small>
--	--	---

2 STUDY OBJECTIVES

2.1 Primary Objective

To assess the efficacy of BoNT/A-DP in reducing the severity of glabellar frown lines following treatment (compared with placebo) based on investigator and subject assessment at week four (of the first treatment cycle).

2.2 Secondary Objectives

1. To assess the proportion of responders at maximum frown and at rest at various time points after each treatment, based on investigator and subject assessments.
2. To assess the psychological impact of BoNT/A-DP treatment on subjects (in terms of emotional and social functioning and concerns relating to their glabellar lines) in comparison with placebo after a single treatment.
3. To assess onset of effect and the duration of effect (at maximum frown) after a single treatment with BoNT/A-DP compared with placebo (first treatment cycle), based on investigator and subject assessments.
4. To provide long term safety data of BoNT/A-DP based on multiple treatment cycles and to establish a sufficient safety database to support regulatory approval.
5. To assess subject perceptions of effect of, and satisfaction with, treatment in comparison with placebo (first treatment cycle) and during the open label extension phase.

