4.5.1.2 Justification for Schedule

The study schedule includes a maximum of four permitted treatments per subject(four treatment cycles), separated by a minimum interval of 12 weeks, during the study time frame of up to 60 weeks in treatment phase. A minimum interval of 12 weeks between treatments was selected, since the median duration of effect has been reported to be 85 days (12.1 weeks) ³¹ and this treatment interval has been evaluated in several repeat treatment studies^{32,33}.

However, since treatment duration of 120 days ³⁴, 17.1± 6.5 weeks ³⁵ or four to six months³⁶have been reported and re-treatment intervals have been estimated at a mean of 3.9 months³⁶, the schedule has been devised flexibly such that subjects can obtain retreatment when they qualify (according to the "Eligibility Criteria for Re-treatment" Section 7.3), which can be at week 12 at the earliest or at four weekly intervals thereafter. Hence, the duration of effect of BoNT/-DP will be evaluated in the first treatment cycle compared with placebo. The duration of effect of BoNT/-DP after repeat treatment will be assessed in the open label extension study. The duration of effect has been reported to increase with repeat treatment³⁷.

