Analysis of additional secondary efficacy endpoint 4: The proportion of subjects with a ≥ 1 point reduction in FWS score at rest at week 4 in the first treatment cycle, based separately on the investigator and the subject in-clinic assessments

In general, the same statistical analyses, inclusive of the additional exploratory analyses as described for the primary efficacy endpoint, will be conducted. However, a sensitivity analysis using a tipping point analysis will not be performed.

All analyses (inclusive the additional exploratory analyses) on the investigators' in-clinic assessment will be conducted only for subjects who have an investigators' in-clinic assessment of a FWS score at rest ≥ 1 at baseline. This will similarly be applied for the analyses of the subjects' in-clinic assessment.

For the primary analysis, subjects with missing investigator in-clinic assessments of FWS score at rest at baseline or week 4 visit will be assigned as being non-responders for this efficacy endpoint. This will similarly be applied for the subjects' in-clinic assessment within the primary analysis.

As a consequence, the primary analysis of this endpoint will lead to exactly the same results as the LOCF analysis (as a subject with missing week 4 is considered as a non-responder) and thus the LOCF analysis will be skipped.

Analyses of other visits after first treatment but before re-treatment up to week 48 are exploratory only based on the FAS population using descriptive statistics only. Subjects with re-treatment before the respective visit will be excluded from the analysis. Additional exploratory analyses, as described for the primary efficacy endpoint, will not be conducted, with the exception of the calculation of 95% CIs.

Other additional secondary endpoint analyses:

Other additional secondary efficacy endpoints will be analyzed applying the appropriate statistical method for the comparison of both treatment arms. For proportions

Statistical Analysis Plan (SAP)

CROMA
est. 1976

- of responders with a FWS score of 0 or 1 and an improvement ≥ 2 points in FWS score at maximum frown (composite endpoint, at weeks 1, 2 and 8),
- of subjects with ≥ 2 and ≥ 1 point reduction in FWS at maximum frown (at baseline and visits 2, 4, 12, 16 and 20 weeks after treatment, within the first treatment cycle),
- of subjects with a ≥ 1 point reduction in FWS at rest, relative to baseline

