- of subjects with an improvement of ≥ 2 points in FWS at maximum frown at 4 weeks after re-treatment,
- of subjects with ≥ 1 point reduction in FWS score at maximum frown (at weeks 1, 2, 4, 8, 12, 16 and 20 relative to baseline,
- of subjects with ≥ 1 point reduction in FWS score at maximum frown at week 4 relative to re-treatment baseline,

the CMH test (with stratification variable site) and the Pearson χ^2 -test will be applied. In case of a total number of observations below 30, or in case of at least one cell frequency below 5, Fisher's exact test will be used instead of the χ^2 -test. Two-sided 95% CIs for response rates will be calculated, where appropriate. Additionally, the cumulative proportions of effects at weeks 1, 2, and 4 will be calculated.

Time to onset of effect in the first treatment cycle will be analyzed descriptively and by using the Kaplan-Meier method. Moreover, the daily assessments of the line severity when frowning will be analyzed descriptively. The FACE-Q satisfaction with outcome scale will be analyzed descriptively.

All efficacy endpoints, with the exception of “responder” 4 weeks after re-treatment, will be analyzed for the first treatment cycle only. The analysis of “responder” 4 weeks after re-treatment will be conducted on observed values only, i.e., subjects with missing investigator or the subject in-clinic assessments on FWS week 4 or at the preceding end of the cycle visit will be excluded from analysis. Subjects who were treated with placebo during the first treatment cycle are excluded from the analysis of this endpoint, but not assigned as being non-responders. A two-sided McNemar test (using a significance level of 0.05) will be used to compare the response proportions between week 4 re-treatment visit and at the preceding end of the cycle visit. These endpoints will be separately analyzed for each open label extension cycle.

In addition to the FAS population, the analyses of these endpoints will also be based on the MFAS and PP populations. For all analyses, a one-sided significance level of 0.025 will be used, if not stated otherwise. Additional exploratory subgroup analyses will be conducted as described in Section 8.8.

Statistical Analysis Plan (SAP)

CROMA
est. 1976

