Visit numbers correspond with specific treatment and assessments as outlined in the protocol Schedule of Events, Section 2.1. If subjects are not eligible for re-treatment at the "Evaluation for Re-treatment" visit, they will return at 4-weekly intervals thereafter, until they are eligible for treatment. The subsequent visit number for the cycle will remain the same, but will be amended with "a, b, c" etc., corresponding to the time extended (at 4-weekly intervals) in that treatment cycle. For example, the first evaluation for re-treatment is at visit 7, week 12; however for subjects who are not eligible at week 12, but at week 16, this visit will be denoted visit "7a", while "visit 7b" will denote week 20 in the first cycle and "visit 7c" will denote week 24 etc., with each additional letter corresponding to a time point 4 weeks later in that cycle. This approach will enable the visit numbers to be standardized, while allowing flexibility to assess the duration of efficacy in the first treatment cycle and in the open label extension.

This visit numbering will be done at SDTM mapping level.

[figure not shown]
Statistical Analysis Plan (SAP)

CROMA
est. 1976

[figure not shown]

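### Duration of effect is a stated cycle 1 objective, but the plan estimates no duration, and its rules for re-treated subjects at late visits are inconsistent

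*SAP*

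**What the plan says.** **What is promised.** SAP 2.2, objective 3, opens "To assess onset of effect and the duration of effect (at maximum frown". The rest of the sentence limits it to one treatment in the first cycle, against placebo, as judged by both raters. Protocol 6.3.1 gives adequate assessment of duration against placebo as the reason for the flexible schedule. For later cycles, Protocol 4.5.1.2 says "The duration of effect of BoNT/-DP after repeat treatment will be assessed in the open label extension study", and SAP Appendix A describes the visit numbering as "allowing flexibility to assess the duration of efficacy in the first treatment cycle and in the open label extension".

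**What is planned for cycle 1.** SAP 4.3 lists responder rates at weeks 12, 16 and 20 or later, and rates of at least 1 point improvement at visits up to week 20. SAP 9 adds a 1-point analysis after week 20. The only time-to-event method is for onset: "Time to onset of effect in the first treatment cycle will be analyzed descriptively and by using the Kaplan-Meier method".

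**What is planned for the extension.** In SAP 8.6.4, all efficacy endpoints other than the responder endpoint "4 weeks after re-treatment, will be analyzed for the first treatment cycle only". SAP 4.3 also has a 1-point rate at week 4 of each re-treatment cycle, and SAP 8.9 repeats the satisfaction scale for all cycles. SAP 8.7.1 summarises exposure days per cycle as a safety table.

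**Rules for re-treated subjects.** SAP 7.2.1 and 8.6.4 count subjects re-treated before week 16 or week 20 as non-responders at maximum frown. For other cycle 1 visits up to week 48, under the at-rest endpoint, SAP 8.6.4 says "Subjects with re-treatment before the respective visit will be excluded from the analysis". SAP 9 gives no rule for the analysis after week 20.

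**The concern.** Half of objective 3, onset, has a matching estimator. The other half, duration, has none. The 4-weekly evaluation visits and the end-of-cycle definition (FWS of 2 or more at maximum frown by both raters) already record the event that a duration analysis needs. As written, the trial could report what proportion still responds at a few visits. It could not report a median duration with a confidence interval, or compare duration across cycles.

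The handling of re-treated subjects adds to this. Under Protocol 7.3, re-treatment requires relapse at maximum frown by both raters. Dropping re-treated subjects therefore removes people because their effect has worn off, and the remaining percentage looks more durable. Two conventions in neighbouring paragraphs, and no convention in SAP 9, would make the late-visit figures hard to read side by side.

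**Working it through.** **1. Is there a duration figure to reproduce?** No. The endpoints in SAP 4.1 to 4.3 and the derived variables in SAP 7.1 contain no duration and no time to loss of effect. SAP 8.6.4 and 8.9 use Kaplan-Meier for onset only.

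**2. Does per-cycle exposure serve instead?** SAP 7.1 ends exposure at the latest of last administration, last visit and end of study. A subject who drops out or reaches study end still in effect contributes days in the same way as one who relapses, so nothing is censored. SAP 3.3 adds a hold on re-treatment from 16 March to 5 May 2020, which lengthened cycles for reasons unrelated to effect. SAP 8.5.1 plans a version without the days between end-of-cycle and re-treatment visits. That removes the hold but not the lack of censoring.

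**3. Effect of dropping re-treated subjects.** Let r be the rate with re-treated subjects counted as non-responders, and f the share re-treated before the visit. Dropping them leaves the numerator unchanged and shrinks the denominator to (1-f), so the rate becomes r/(1-f).

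| Assumed f | Factor 1/(1-f) |
|---|---|
| 30% | 1/0.70 = 1.43 |
| 50% | 1/0.50 = 2.00 |
| 70% | 1/0.30 = 3.33 |

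The documents give no f, so this is a range of assumptions. The factor compares two counting conventions. Relapse is defined at maximum frown, so a re-treated subject need not have lost the effect at rest.

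**4. How many subjects would inform a duration estimate?** Inputs: 353 enrolled, 3:1 allocation, and week 4 response of 46% and 2% (SAP 5).
- Active: 353 x 3/4 = 265; week 4 responders 265 x 0.46 = 122.
- Placebo: 353 x 1/4 = 88; week 4 responders 88 x 0.02 = about 2.
- Standard error of a proportion near 50% among 122 responders, ignoring censoring: sqrt(0.25/122) = 4.5 percentage points.

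A median among active responders is therefore estimable. A placebo median among responders is not. If week 4 non-responders are assigned zero duration, 54% of the active arm would have zero. The FAS median would then be zero in both arms, so the placebo comparison has to be read from the whole distribution.

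**5. Visit grid.** In cycle 1, FWS is collected at weeks 1, 2, 4, 8, 12 and every 4 weeks after that. In open-label cycles it is collected at week 4 and then from week 12; weeks 2 and 8 are telephone calls (Protocol 2.1). The gap matters. In the first earlier trial (Protocol 4.4.2.1), half the week 4 composite 1-point rate is 81.5/2 = 40.8%, between the week 12 rate (45.1%) and the week 16 rate (20.8%). In the second (Protocol 4.4.2.2), half is 83.1/2 = 41.6%, already above the week 12 rate (40.5%), so the halving point falls between weeks 4 and 12. This is a rough guide from visit-wise rates on a different endpoint.

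**The case against.** The strongest reply is that persistence visit by visit against placebo is a recognisable way to address objective 3. Cycle 1 has responder rates at weeks 12, 16 and 20 or later, 1-point rates from week 1 to week 20, and a 1-point analysis after week 20. The earlier trials described maintenance of effect in this way. This stands in part: cycle 1 does have a coarse picture of persistence, and a reader who inferred that nothing in the plan bears on duration would go too far.

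Three other stronger readings are not supported:
- **That duration in the extension is a numbered objective.** Objective 3 is limited to the first cycle. Extension duration is an intention stated in the schedule rationale and the visit-numbering text. Objective 1 does reach each treatment, but for responder proportions.
- **That the exclusion rule distorts the week 16 and 20 results at maximum frown.** It is exploratory and descriptive, stands under the at-rest endpoint and covers other visits. The matching sentence in Protocol 12.4.2 concerns responders and has no exclusion, so its scope needs stating.
- **That the remaining responders would be most of the denominator.** The rule drops re-treated subjects; those relapsed but not yet re-treated stay in. Even with the first earlier trial's 9.9% at week 20, a visit this rule does not govern, 0.099/(1-f) > 0.5 needs f above 80%.

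A simple time-to-event analysis in the FAS would also fail. Every subject enters with FWS of 2 or 3 by both raters, so anyone without effect yet at week 1 would be an event at week 1, and the test would largely restate onset and response. The remedy has to avoid this.

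**Conclusion.** The point holds in this form. A stated cycle 1 objective has no duration estimator, only proportions by visit. The stated intention for the extension has only week 4 FWS efficacy and uncensored exposure days. Late-visit handling of re-treated subjects is inconsistent between paragraphs of SAP 8.6.4 and undefined in SAP 9. Where they are dropped, a late-visit rate is about 1.4 to 3.3 times the rate under the non-responder convention, for an assumed f of 30% to 70%. The primary endpoint, the key secondary hierarchy and the week 16 and 20 responder analyses are not affected. The expected 122 active responders rest on the plan's own 46% and on full enrolment of 353.

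**What to change.** Add to SAP 8.6.4, as exploratory:

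1. **Cycle 1, active arm, week 4 composite responders.** Estimate time from injection to the first visit after week 4 with maximum-frown FWS of 2 or more by both raters. Treat it as interval-censored on the visit grid, censor at discontinuation or end of study, and report the median with a 95% CI.
2. **Cycle 1, comparison with placebo.** Use the FAS with week 4 non-responders assigned zero duration, because few or no placebo subjects will respond. Show the proportion still in effect over time; the FAS medians would probably both be zero.
3. **Each open-label cycle.** Repeat item 1 descriptively. Compare cycles only on the common grid of week 4 and then week 12 onward. Define the event by FWS and not by the re-treatment date, so that the 2020 hold does not lengthen it, and flag remote assessments.
4. **Late-visit summaries.** State the scope of the exclusion rule in SAP 8.6.4. There, and in the analysis after week 20 in SAP 9, count subjects re-treated before the visit as non-responders, as at weeks 16 and 20.

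Items 1 to 3 belong to the final analysis, because the interim data stop at week 16.

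**Cost.** SAP wording, one table and one figure from data already collected. There is no cost in alpha, since SAP 8.6.1.1 treats everything outside the hierarchy as exploratory. The limits to state are 4-week resolution in cycle 1 after week 4 and an 8-week gap between weeks 4 and 12 in open-label cycles.
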